All major variables will be screened for inconsistent or abnormal values, and continuous measures will be assessed for skewness and outliers. Transformations to improve normality may be applied to continuous variables. Missing data rates and patterns will be assessed; in particular, missing data rates by treatment group will be studied. Although randomization tends to produce well-balanced treatment samples⁵⁹ analyses will be carried out to determine any baseline differences between the treatment groups on demographic or other prognostic variables, using chi square analyses for discrete variables and ANOVA for continuous ones. If significant treatment group differences are found on potentially important baseline variables, these variables will be covaried in outcome analyses. Data from all randomized study participants will be used to compare the outcome of the two interventions on an intent-to-treat basis. Hypothesis tests will be two-tailed.

Participants will be counted in the intervention group to which they were randomized, regardless of the number of sessions they completed. We will make every attempt to complete a post-treatment and 3 and 6 month follow-up assessments on any participants who do not complete treatment. We will also conduct supplementary analyses including only those cases completing the full 12 sessions.

Aim 1: Investigate the effectiveness of CBI on primary measures of outcome

Hypothesis: Compared to SI, CBI will be associated with significantly larger reductions in anger and aggressive behaviors at post-treatment and at 3 and 6 month follow-ups.

Aim 2: Investigate the effectiveness of CBI on secondary measures of outcome

Hypothesis: Compared to SI, CBI will be associated with significantly more improvement in social functioning, occupational functioning, quality of life, and PTSD symptoms at post-treatment and at 3 and 6 month follow-ups.

For aims 1 and 2, we will use hierarchical linear modeling (HLM) for repeated measures to test for differences due to treatment condition, covarying for the baseline score of the dependent variable⁶⁵. The primary significance test will be the treatment group main

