effect over time, though there will also be a test for the time by treatment interaction. Significant time by treatment interactions will be followed up by post hoc tests at specific assessment points by calculating simple intercepts, simple slopes, and regions of significance. Relevant covariates will be included to adjust for any imbalances across treatment conditions.

Missing data will be dealt with as follows. HLM analyses can include cases with some time points missing. In the primary analysis, we will include all cases with at least 3 of the 5 outcome time points (4 & 8 weeks, posttreatment, and 3 & 6 months) non-missing. Then, we will conduct a sensitivity analysis including all randomized participants, in which any missing outcome values will be filled in with baseline scores, which is an extreme assumption. Consistency of results from the two approaches will bolster the credibility of the primary analysis.

The primary dependent variables for aim 1 are the STAXI-2 Anger Expression Index, and the OAS-M Aggression Scale score. Outcome on these measures is assessed at 4 and 8-week points during treatment, at post-treatment, and at 3 and 6 months follow-up assessments. DVs for aim 2 include two LIFE scales (global social and work functioning), the Outcomes Questionnaire total score, the WHOQOL-BREF total score, and the CAPS total score. Outcome on these measures is assessed at post-treatment and 3 and 6-month follow-up assessments.

For aims 1 and 2 the alpha will be set at .025 to account for multiple dependent variables.

Supplementary post-treatment outcome analyses will be conducted using collateral measures (including the STAXI-II, Anger Control Scale and Modified Overt Aggression Interview). We will calculate Pearson correlations of participant and collateral scales as an indication of agreement. If outcome analyses based on collateral measures are consistent with analyses of participant measures, this would bolster the validity of the participant outcome findings. Divergent findings could be due to multiple factors that could influence the validity of the participant and the collateral reports. In this case we will conduct analyses using integrated collateral and participant scores, calculated by averaging the participant and collateral responses to each item.

Aim 3: (Exploratory) Examine hypothesized mechanisms of action of CBI

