Hypothesis: Change in arousal, cognitive, and behavioral domains of anger will mediate outcome for anger and functioning in the CBI condition.

In order to examine the mediating role of arousal, cognition, and behavior (NAS scales), we will use arousal, cognition, and behavior at post-treatment as mediators of the effect of treatment in predicting later anger and functioning at months 3 and 6. Therefore, these mediation tests will be fully prospective, as recommended by Kazdin & Nock⁶⁶, and as exemplified in prior mediational research done by [name]. These analyses will covary for the baseline scores of the mediators. Mediation of treatment effects through NAS scales will be tested using the Sobel test^{69, 70}. Simulation tests indicate that we will have more than 80% power to detect mediation when both paths have small to medium effect sizes⁷¹.

Aim 4: (Exploratory) Examine the effectiveness of CBI for those with and without PTSD. We will test for an interaction between CBI vs. SI and PTSD status by calculating simple slopes. Since we will not have 80% power to test this interaction, we will calculate treatment effect sizes separately for the PTSD and the no-PTSD cases.

G.3. Power Analysis

Power for our repeated-measures design was estimated using methods described by Faes et al.⁷¹. We obtained intervention effect sizes ranging from 0.78 to 1.12 in our pilot study, but given the small sample and the instability of effect sizes derived from pilot studies⁷² we have conservatively based our statistical power analysis for detection of medium effects.

We will use a two-sided alpha level of .025 in the primary and secondary outcome analyses to correct for the number of dependent variables; i.e., each DV will be tested individually with an alpha level of .025, keeping the study-wise alpha at .05. With this alpha level and an estimated 80% follow-up, a sample size of 120 will provide 90% power to detect a medium effect size of .60.

H. Time-Line

We anticipate the following time-line for the study:

Months	
0-6 Hiring, Training, IRB approvals	12-42 Follow-Up (6 month)
6-33 Recruitment	6-43 Data Entry and Management
6-36 Treatment	43-48 Final Data Analyses and Manuscript
9-39 Follow-Up (3 month)	Writing

I. Dissemination and Future Plans

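### Aim 3 (exploratory): the claim of more than 80% mediation power gives no inputs, and the design does not support it across a small-to-medium range

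*Combined protocol and SAP*

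**What the plan says.** Section 4.G.2 labels the aim exploratory: "Aim 3: (Exploratory) Examine hypothesized mechanisms of action of CBI". The three NAS subscales at post-treatment are the mediators, and anger and functioning at months 3 and 6 are the outcomes. The test is named: "Mediation of treatment effects through NAS scales will be tested using the Sobel test". One kind of covariate is named: "These analyses will covary for the baseline scores of the mediators". The power statement follows: "Simulation tests indicate that we will have more than 80% power to detect mediation when both paths have small to medium effect sizes". Its only support is superscript 71.

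Section 4.G.3 gives inputs for the primary and secondary outcome analyses only. On alpha: "We will use a two-sided alpha level of .025 in the primary and secondary outcome analyses". On size: "an estimated 80% follow-up, a sample size of 120 will provide 90% power to detect a medium effect size of .60". No alpha is set for Aim 3.

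Aim 4, also exploratory, is handled differently: "Since we will not have 80% power to test this interaction, we will calculate treatment effect sizes separately" for participants with and without PTSD.

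**The concern.** The sentence cannot be checked from the plan, because none of the quantities that fix the power of an indirect-effect test is given. It also looks optimistic. The Sobel test is conservative when both paths are modest, and about 96 participants is a small sample for a product of two modest paths.

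What is at stake is how a null result would be read. Set against a stated power above 80%, a non-significant indirect effect would look like evidence against the arousal, cognitive and behavioural mechanisms. If true power at mid-range paths is far lower, such mediation would usually be missed and the null would say little. Aim 4 warns the reader that power is short; Aim 3 gives the opposite assurance.

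**Working it through.** **The plan's own figures.** The mediation figure cannot be reproduced, for want of inputs. The section 4.G.3 figure can be used to infer a precision. With 80% of 120 = 96 followed (48 per arm, 1:1 assumed), d=.60 and two-sided .025, a plain two-group comparison has about 76% power, so the stated 90% needs a gain from repeated measures or covariates. The implied standard error of d is .60/(2.241+1.282) = .170. The plain value is sqrt(4/96) = .204. The variance ratio is .696 = 1-.55², so a baseline correlation of about .55 would give the same precision.

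**Sobel power.** Let ta be the test statistic for the treatment-to-NAS path and tb that for the NAS-to-outcome path. Then z = ta·tb/sqrt(ta²+tb²), which is always smaller in size than either ta or tb. Sobel power therefore cannot exceed the power of the weaker path alone.

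Assumptions: two-sided .05, normal errors, d on the SD scale, r the partial correlation given treatment and baseline mediator, and k the baseline-mediator correlation.
- ta is centred at d/(.204·sqrt(1-k²)).
- tb is centred at r·sqrt(96-4)/sqrt(1-r²) for one visit. Averaging months 3 and 6 (assumed residual correlation .5) multiplies the outcome residual variance by (1+.5)/2 = .75, so tb is divided by sqrt(.75).

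**Cap that does not depend on the treatment path.** At r=.2, tb = .2·sqrt(92)/sqrt(.96) = 1.96 for one visit and 1.96/.866 = 2.26 averaged. The power of that path alone is P(|N(tb,1)| > 1.96) = 50% or 62%. With all 120 followed it is 59% or 72%. These caps use only the covariates Aim 3 names.

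**Sobel power over k** (96 followed; each cell is one visit / averaged; figures good to about one point):

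| Assumed paths | k=0 | k=.5 | k=.7 | k=.8 |
|---|---|---|---|---|
| d=.35, r=.2 | 6 / 9% | 9 / 12% | 14 / 19% | 21 / 28% |
| d=.5, r=.3 | 36 / 45% | 47 / 57% | 62 / 73% | 72 / 84% |
| d=.60, r=.3 | 50 / 61% | 61 / 72% | 73 / 84% | 79 / 89% |

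**If the implied SE of .170 is assumed to hold for the NAS:**
- d=.2, r=.1: under 1%.
- d=.35, r=.2: about 10% (one visit) and 13-14% (averaged).
- d=.5, r=.3: 50% and 61%.
- d=.60, r=.3: 64% and about 75%.
- At d=.60, 80% needs r of about .36 (one visit) or .32 (averaged).

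**Favourable variants.**
- Also adjusting for the baseline outcome (correlation .5), with k=.7 and averaging: 26% at d=.35, r=.2; 82% at d=.5, r=.3; 92% at d=.60, r=.3.
- For d=.35, r=.2 with k=.8, averaging and a baseline-outcome correlation of .7: 51% at 96 followed. With all 120 followed as well, ta = .35/(sqrt(4/120)·.6) = 3.20 and tb = .2·sqrt(116)/sqrt(.96·.75·.51) = 3.55, which gives about 70%.
- For d=.40, r=.3 with all 120 followed, k=.8 and averaging: 85%.

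**Unfavourable variant.** At two-sided .025 and the implied SE, d=.35, r=.2 falls to 3-6%.

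**Alternative test** (96 followed, k=.5, one visit). A Monte Carlo interval for the indirect effect gives 66% against 47% for Sobel at d=.5, r=.3, and 22% against 9% at d=.35, r=.2. Type I error with one path null and the other at d=.5 or r=.3 is about 4% against about 1%. For the Monte Carlo interval it reaches 5.7% when the other path is very large.

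**The case against.** The strongest reply is that no error is shown. The sentence points to a source by superscript, and how that source scales small to medium cannot be seen here. The pairing of a standardized difference for one path with a partial correlation for the other is this review's choice, as are d=.35 and r=.2. This stands: a reader might infer that the plan miscalculated, and the documents do not support that.

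A reader might also take 10-14% as the power at mid-range. That is too precise. It carries an SE from the Aims 1 and 2 analysis, with up to five visits per outcome and "covarying for the baseline score of the dependent variable", over to a single post-treatment NAS score. Other reasonable correlations move the same cell from 6% to 28%, and the extra gains listed move it further. The plan also calls .60 medium, so a midpoint of d=.40 is arguable. At the implied SE with r=.2 to .3 that gives 13-33% (one visit) or 18-42% (averaged), still well below 80%.

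Nor do the figures show that 80% is confined to the very top of the range: d=.40, r=.3 reaches 85% under favourable correlations with full follow-up.

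Finally, the Sobel test is valid, only conservative, so replacing it is a gain in power and not a correction. Changing a named test late also needs safeguards.

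What the reply does not remove is the cap at r=.2, which holds for any treatment effect on the NAS, or the absence of any stated limit in the sentence.

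**Conclusion.** Minor: a shortfall in power justification and reporting, not a proven arithmetic error. The claim of more than 80% states no inputs and is not supported across a conventional small-to-medium range. At 96 followed, two-sided .05 and the covariates Aim 3 names, Sobel power at r=.2 cannot exceed about 50% or 62%. Assumed mid-range paths give about 6-28%, and at most about 51% with the favourable gains tried at that follow-up. Paths of d=.5 to .60 with r=.3 give about 36-89%, so 80% is attainable toward the upper end or with favourable correlations and follow-up.

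All path values, correlations and the .05 level are assumptions, because the plan gives none for Aim 3. Confidence is high that mid-range power falls short of 80%, and low for any single figure. No sample size, primary test or primary conclusion depends on this sentence.

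**What to change.** 1. Delete the 80% sentence and report each indirect effect as an estimate with a confidence interval, in the spirit of Aim 4. This is the simpler course, since the version date (11/28/18) falls after the planned study end (07/31/2018). Otherwise restate the power with path values and their scale, alpha, number followed and assumed correlations, and limit the claim to paths that reach 80%.
2. Replace the Sobel test with a Monte Carlo or bootstrap interval for the indirect effect. Record this as a dated change before Aim 3 results are seen, and keep Sobel as a secondary report if wanted.
3. Check the citation. Superscript 71 leads to a paper on effective sample size, while reference 70 concerns sample size for mediated effects. This is probably a clerical numbering slip.

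Cost: wording and a little analysis time, with no new data. The Monte Carlo interval uses coefficients and standard errors that the planned models already produce. The stated power becomes less favourable or disappears. Type I error with one null path rises from about 1% to about 4%, and to as much as 5.7% when the other path is very large.

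### Testing every primary and secondary outcome at .025 does not hold the study-wise alpha at .05: seven outcomes are tested, and the arithmetic covers two

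*Combined protocol and SAP*

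**What the plan says.** The error-rate claim is in section 4.G.3 (Power Analysis): "We will use a two-sided alpha level of .025 in the primary and secondary outcome analyses to correct for the number of dependent variables". The same sentence goes on to say that "each DV will be tested individually with an alpha level of .025, keeping the study-wise alpha at .05".

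Section 4.G.2 (Data Analysis) gives the matching rule: "For aims 1 and 2 the alpha will be set at .025 to account for multiple dependent variables". It also fixes the number of DVs:

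- Aim 1: "The primary dependent variables for aim 1 are the STAXI-2 Anger Expression Index, and the OAS-M Aggression Scale score". That is two.
- Aim 2: "DVs for aim 2 include two LIFE scales (global social and work functioning), the Outcomes Questionnaire total score, the WHOQOL-BREF total score". That is four; total CAPS severity is listed as the fifth.

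The tests are two-sided ("Hypothesis tests will be two-tailed"). For each DV the main significance test is the treatment effect over time, and a time-by-treatment test is also planned. No part of section 4.G puts the tests in order, makes the secondary tests depend on the primary ones, or gives Aim 2 its own multiplicity procedure.

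**The concern.** Splitting .05 into two halves is the Bonferroni level for two tests. The claim attached to it covers the secondary analyses as well, which brings the count to seven.

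What is at stake is how Aim 2 is read. Aim 2 is stated as a hypothesis of superior improvement in functioning, quality of life and PTSD symptoms. Unlike Aims 3 and 4, it is not labelled exploratory. On the plan's wording, a secondary result with p < .025 could be reported as protected at a study-wise .05 when it is not. The primary conclusion, Aim 1 and the sample size do not depend on this point.

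**Working it through.** **Inputs from the protocol.** Per-DV level .025, two-sided (4.G.3). Claimed study-wise level .05 (4.G.3). Two primary and five secondary DVs, seven in all (4.G.2).

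**Assumption.** The documents give no correlation between outcomes. A common correlation r between the test statistics is assumed, with r = 0, .5 and .7 as the main range. One test is counted per DV (the treatment main effect), and all null hypotheses are taken as true.

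**Reproducing the plan's figure.** For k tests the Bonferroni bound is k × .025. With k = 2 it is 2 × .025 = .05, as the plan states. If the two are independent, the exact rate is 1 − .975² = .0494.

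**Applying it to the stated scope.**

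- Aim 2, k = 5: bound 5 × .025 = .125; independent, 1 − .975⁵ = .119.
- Both aims, k = 7: bound 7 × .025 = .175; independent, 1 − .975⁷ = .162.

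**Effect of correlation.** The correlated columns come from simulating equicorrelated normal statistics (1,000,000 draws). Two-sided family-wise error:

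| Family | Bound | r = 0 | r = .5 | r = .7 |
|---|---|---|---|---|
| Two primary DVs | 5.0% | 4.9% | 4.6% | 4.3% |
| Five Aim 2 DVs | 12.5% | 11.9% | 9.8% | 8.0% |
| All seven DVs | 17.5% | 16.2% | 12.6% | 9.8% |

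Against .05, the seven-DV rate is 16.2/5 = 3.2 times at r = 0 and 9.8/5 = 2.0 times at r = .7. For Aim 2 alone the multiples are 2.4 and 1.6.

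**Higher correlation.** The seven-DV rate is 8.1% at r = .8 and 6.2% at r = .9. It reaches .05 only near r = .95 (4.9%).

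**Errors in CBI's favour only.** Because the tests are two-sided, the rates above are the ones to compare with .05. The chance of at least one false finding favouring CBI is about half: 8.4%, 6.3% and 4.9% over seven DVs, and 6.1%, 4.9% and 4.0% over Aim 2, at r = 0, .5 and .7.

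**The case against.** The strongest case on the other side has four parts.

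- **Secondary outcomes need no adjustment.** The plan separates primary from secondary outcomes clearly, and leaving secondaries unadjusted is a legitimate choice. This is right as far as it goes, and the first remedy below accepts it. The plan does not make that choice, though: it names the secondary analyses and claims control over them.
- **Study-wise may have meant per aim.** That reading rescues Aim 1 only. Five tests at .025 have a bound of .125.
- **The upper figures are pessimistic.** 16.2% needs uncorrelated outcomes and no effect of CBI on any of the seven DVs. Scores from the same people will be correlated, and at r = .9 the excess is small (6.2% over seven DVs, 5.4% over Aim 2). The size is therefore uncertain. But a common correlation near .95 across self-report and interviewer-rated measures of different constructs is not plausible, so the excess remains.
- **Timing.** The protocol gives a study end date of 07/31/2018, and this version is dated 11/28/18. The documents do not say whether outcomes had been analysed. Changing secondary thresholds after outcomes by arm are known would create a new problem. This stands, and it favours the remedy that changes no threshold.

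A further qualification concerns the primaries. Their control is sound for the main-effect tests. If the time-by-treatment tests were also counted at .025, the bound for the two primary DVs would be 4 × .025 = .10, so the corrected sentence should name the main-effect tests.

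**Conclusion.** The concern holds. The study-wise .05 statement is wrong for the scope the plan gives it and right only for the two primary DVs. With seven DVs at two-sided .025, the family-wise error is about 10% to 16% for correlations from .7 down to 0, with a bound of 17.5%. For Aim 2 alone it is about 8% to 12%, with a bound of 12.5%. The count of DVs and the bounds follow from the protocol alone; the rates below the bounds rest on the assumed common correlation. The interaction tests are left out, which makes the count conservative. The two primary main-effect tests, Aim 1 and N = 120 are unaffected.

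**What to change.** Keep .025 for each primary DV and limit the .05 statement to the two primary main-effect tests. Then choose one of these for Aim 2.

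**(a) Declare the Aim 2 tests nominal.** State that the five secondary tests are not controlled for multiplicity. This costs one sentence and changes no test or threshold, so it is safe whatever the state of the data. It is the better choice unless outcomes by arm are still unseen.

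**(b) Apply Holm across the five Aim 2 DVs.**

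- *Gated:* family alpha .05 if both primaries are significant, .025 if one is, and no confirmatory claim if neither is. In simulation (r = 0, .3, .5, .7; zero, one or two truly effective primaries) family-wise error over both aims was at most .05.
- *Ungated:* Holm at .05, with control claimed only within each aim. Error across both aims together is then 9.6% to 6.2% for r = 0 to .7.

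At family alpha .05 the Holm steps are .01, .0125, .0167, .025 and .05: three stricter than now, one equal and one looser. With one primary significant they run from .005 to .025.

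The cost of (b) is power on Aim 2. If an Aim 2 DV had 90% power at .025, its noncentrality would be 1.282 + 2.241 = 3.523. First-step power would then be Φ(3.523 − 2.576) = 83% at .01 and Φ(3.523 − 2.807) = 76% at .005, before allowing for the gate staying closed. The documents do not support that 90% for Aim 2. Primary DVs have five outcome assessments, while for Aim 2 "Outcome on these measures is assessed at post-treatment and 3 and 6-month follow-up assessments", which is three. If the 90% was computed for five, and the effect size is the same with an exchangeable residual correlation of .3 to .7, the variance of the treatment effect rises by a factor of 1.21 to 1.05. Power then becomes 83% to 88% at .025, 73% to 80% at .01 and 65% to 73% at .005. Under (b), Aim 2 power should therefore be computed separately. Neither option affects Aim 1 or N.
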